7.5 Pharmacodynamics

Tissue and blood samples will be collected to understand the pharmacodynamic effect of PCLX-001.

7.5.1 Tissue Samples

Archived tissue samples will be requested from all patients and pre-treatment biopsies will be optional for patients enrolled in whom an archival biopsy is older than 6 months. These will be collected for response prediction analyses and exploratory research. Archived tumour blocks will be returned to the clinical investigator at the end of the study or, if requested, once sections have been obtained for biomarker analysis.

7.5.2 Blood Samples

Collection of blood samples for exploratory biomarker research is also a part of this trial. Blood samples will be collected from all patients in this study as specified in the Schedule of Evaluations (Table 7A and 7B). Specimens will be stored and may be used for research purposes to identify biomarkers useful for predicting and monitoring PCLX-001.

8. STATISTICAL CONSIDERATIONS

8.1 Sample Size Determination

The exact sample size for Part A dose-escalation cannot be pre-determined and depends on the number of cohorts needed to reach MTD. Part A will enroll at least 9 patients and up to 52 patients. In Part B, there are two expansion cohorts of 20 patients each for a total of 40 patients.

8.2 Populations for Analyses

Table 8-1: Analysis Populations

Population	Description
Efficacy	All participants who received at least one dose of PCLX-001 and had at least one on-treatment tumour assessment will be included in the efficacy analysis.
Safety	All participants who received at least one dose of study treatment, whether prematurely withdrawn from the study or not, will be included in the safety analysis.
MTD-determining population (Part A only)	All participants from the safety analysis population who follow the protocol-specified dose regimen within the DLT observation period and have undergone the scheduled safety evaluations, or who discontinued earlier due to a DLT, will be included in the MTD-determining analysis.
Pharmacokinetic	All participants who have received at least one dose of study treatment and who have data from at least one post-dose sample will be included in the PK analysis population. Participants will be excluded from the PK analysis population if they significantly violate the inclusion or exclusion criteria or deviate significantly from the protocol or if their data are unavailable or incomplete, which may influence the PK analysis. Excluded cases will be documented together with the reason for exclusion.

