Table 7B: Schedule of Evaluations (Study Flow Chart) – TREATMENT AND FOLLOW-UP

Measures / actions	Treatment ⁿ								FU	
	Cycle 1					Cycle 2		Cycle ≥ 3	EOT visit	Safety FU visit ^b
	D1 ^a	D2	D8	D15	D22	D1	D15	D1		Long-Term FU ^o
Before study drug administration										
Check of inclusion / exclusion criteria	X									
Abbreviated medical history	X		X	X	X	X	X	X	X	
Concomitant medications ^c	X		X	X	X	X		X	X	
Assessment of toxicities (AEs) ^d	X		X	X	X	X	X	X	X	
12-lead ECG (standard, triplicate)	X					X			X	X
Blood pressure, heart rate, & body temperature	X		X	X	X	X	X	X	X	
Physical examination ^l	X		X	X	X	X		X	X	X
Body weight	X		X	X	X	X	X	X	X	X
ECOG performance status assessment	X		X	X	X	X	X	X	X	X
Blood sample collection for biomarker analysis ^f	X					X		X	X	
Blood / urine sample collection for laboratory safety assessments										
• Hematology ^g	X		X	X	X	X	X	X	X	
• Blood chemistry ^h	X		X	X	X	X	X	X	X	
• Calculation of eGFR by Cockroft-Gault	X					X				
• Coagulation (aPTT; PT/INR)	X					X				
• Thyroid function (TSH and T ₄ [total or free per local standard])	X					X			X	
• Virology (HBV DNA, HCV RNA) ^m	X									
• Pregnancy test (serum or urine) ^j	X									
• Urinalysis (dipstick)	X			X		X			X	
Tumor assessment all tumors (CT or MRI) ⁱ							End of every second cycle			
PET-CT (optional, NHL patients only) ^k							Once after sixth cycle			
Blood sample collection for tumor marker, if applicable (e.g., CA125, CEA, PSA)							End of every second cycle			
Survival status										X ^o

Table 7B: Schedule of Evaluations (Study Flow Chart) – TREATMENT AND FOLLOW-UP (continued)

Measures / actions	Treatment								FU
	Cycle 1					Cycle 2		Cycle \geq 3	
	D1 ^a	D2	D8	D15	D22	D1	D15	D1	
Study drug administration									
Review of patient study medication diary and compliance of medication taken at home	X	X	X	X	X	X	X	X	
PCLX-001 administration at study center	X	X	X	X	X	X	X	X	
Before & after study drug administration									
PK sampling (plasma) for PCLX-001 ^e escalation	X	X	X	X	X	X	X	X	
PK sampling (plasma) for PCLX-001 ^e expansion	X			X		X		X	

- a. Any of the assessments scheduled before drug administration on C1D1 may be missed without protocol deviation if the same assessment has been obtained and reviewed within 3 days before the start of treatment (except PK and exploratory biomarker analysis).

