- b. If a patient discontinues study treatment at any time during the study for any reason (except for patients who died, withdrew consent and objected to further data collection, or were lost to FU), an active FU assessment should be performed 30 days (± 4 days) after the last dose of the last study drug.
- c. Prescribed and OTC.
- d. Questioning for AEs will be conducted at clinic visits; in addition, spontaneous reports of AEs will be collected throughout the study.
- e. PK sampling: For patients in dose escalation, see Table 7C for schedule. For patients in dose expansion, see Table 7D for schedule.
- f. To be taken pre-dose of each cycle Day 1 within 60 min before the morning dose and EOT
- g. Hematology includes CBC + differential (i.e. hemoglobin erythrocytes, leukocytes, platelets, MCV, RDW, hematocrit, neutrophils, lymphocytes, monocytes, eosinophils, basophils, immature granulocytes, nucleated RBCs). Detection of CTCAE Grade 4 neutropenia (only Cycle 1) will trigger twice-weekly white blood cell counts to be performed, so that DLT determination can be made.
- h. Blood chemistry includes: sodium, potassium, chloride, bicarbonate or total CO² (as per site practice), calcium, phosphate, magnesium, total protein, albumin, glucose, serum creatinine, urea, uric acid, total bilirubin, ALT, AST, LDH, alkaline phosphatase, lipase.
- i. Window for tumour assessment is ± 5 days from Day 28 of the even-numbered cycles. CT of the relevant disease region for solid tumors and CT thorax, abdomen, pelvis \pm neck for NHL.
- j. Women of childbearing potential (including women of childbearing potential whose partners are sterilized) must have a negative pregnancy test.
- k. This scan should only be performed for NHL patients and is optional (i.e. not required for patients with other histologies). If a PET-CT is performed at screening, it should be repeated once after the sixth cycle if no progressive disease is detected during the course of treatment and / or to confirm complete response or disease progression.
- l. Exam to be symptom-directed.
- m. To be performed if clinically indicated (e.g. positive HBsAg and/or anti-HCV tests as performed during screening).
- n. Unless otherwise indicated, the window for visits is ± 2 days.
- o. Electronic records will be used to assess patient survival monthly (± 1 week) from the date of the follow-up visit.

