7.3 Determination of Efficacy Outcomes

Tumor response and progression of solid tumors and NHL will be evaluated by the investigator at each study center consistent with RECIST 1.1 criteria (see [Appendix B](#)), or Lugano Classification of Lymphoma response (see [Appendix C](#)).

Tumor markers can play a role in detecting disease and assessing response to therapy in selected groups of patients. In monitoring patients for disease progression, tumor marker levels should be determined according to clinical practice (e.g., CA125 for ovarian cancer, CEA for colorectal cancer, PSA for prostate cancer).

Solid Tumors

In *measurable* lesions (i.e. at the primary site, visceral [≥ 1.0 cm long axis], or nodal [in lymph nodes ≥ 1.5 cm short axis] lesions), the objective response will be assessed by contrast-enhanced CT or MRI and documented consistent with RECIST 1.1 criteria (see [Appendix B](#)). Tumor measurements for efficacy evaluation will be made every 2 cycles, beginning with a baseline scan and unless progression is noted, all lesions will be assessed and reported at the end of every second cycle, starting at the end of Cycle 2.

Non-Hodgkin's Lymphoma

Efficacy will be assessed based on radiological tumor evaluations, which will include neck, chest, abdomen, and pelvis by contrast-enhanced CT / MRI scans. PET-CT can be utilized throughout the study if it is considered standard of care at the institution. Scans will be performed as shown in Table 7A and Table 7B and will be evaluated locally at the study site.

PET-CT is optional in this study and should be done based on institutional standards whereas the CT portion of the PET-CT should be of diagnostic quality, i.e. appropriate radiation dose and contrast enhancement. In case the CT portion of the PET-CT is performed for attenuation correction only an additional whole body CT in diagnostic quality is needed. If a PET-CT with a PET positive finding was performed at screening an interim PET-CT should be done after the sixth cycle. For any imaging follow-up after interim PET-CT it is recommended to confirm any changes in previous metabolic overall response that were assessed with CT alone with PET-CT.

Response assessment will be based on the Lugano Classification (see [Appendix C](#)).

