8.4 Statistical Analyses

Descriptive statistics will be utilized to present study patient population and toxicity data.

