Appendix B. Response Evaluation Criteria In Solid Tumors (RECIST Version 1.1)

The following information is extracted/summarized from Eisenhauer, 2009, New Response Evaluation Criteria in Solid Tumors: Revised RECIST Guideline (Version 1.1). Please refer to the primary reference for further information.

Definitions

At screening, tumor lesions/lymph nodes will be categorized as measurable or non-measurable.

Measurable Disease

Tumor Lesions. Must be accurately measured in at least one dimension (longest diameter in the plane of measurement is to be recorded) with a minimum size of:

- 10 mm by CT scan (CT scan slice thickness no greater than 5 mm)
- 10 mm caliper measurement by clinical exam (lesions which cannot be accurately measured with calipers should be recorded as non-measurable)
- 20 mm by chest X-ray

Malignant Lymph Nodes. To be considered pathologically enlarged and measurable, a lymph node must be ≥ 15 mm in short axis when assessed by CT scan (CT scan slice thickness recommended to be no greater than 5 mm). At baseline and in follow-up, only the short axis will be measured and followed.

Non-measurable Disease

All other lesions, including small lesions (longest diameter <10 mm or pathological lymph nodes with ≥ 10 to < 15 mm short axis) as well as truly non-measurable lesions. Lesions considered truly non-measurable include: leptomeningeal disease, ascites, pleural or pericardial effusion, inflammatory breast disease, lymphangitic involvement of skin or lung, abdominal masses/abdominal organomegaly identified by physical exam that is not measurable by reproducible imaging techniques.

Choosing Target Lesions

- Select up to 5 lesions (up to 2 per organ).
- Select largest reproducibly measurable lesions.
- If the largest lesion cannot be measured reproducibly, select the next largest lesion which can be.
- Add up longest diameters (LD) of non-nodal lesions (axial plane).
- Add short axis diameters of nodes.
- This is the sum of the longest diameters (SLD).

Nontarget Lesions

- All other sites of disease present at baseline and not classified as target lesions will be classified as nontarget lesions, including any measurable lesions that were not chosen as target lesions.
- It is possible to record multiple nontarget lesions involving the same organ as a single item on the eCRF (eg, “multiple enlarged pelvic lymph nodes”).

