- Measurements are not required but these lesions should be noted at baseline and should be followed as “present,” “absent,” or “unequivocal progression.”

Determining Response

- Assess at baseline and on study with consistent modalities (CT, MRI, PET/CT).
 - Measure target lesions and calculate SLD.
 - Visually assess nontarget lesions.
 - Search for new lesions.
 - Combine these assessments into the overall response.

Target Lesion Response

Complete response (CR)	
• Disappearance of all extranodal target lesions.• All pathological lymph nodes must have decreased to <10 mm in short axis.
Partial response (PR)	
• At least a 30% decrease in the SLD of target lesions, taking as reference the baseline sum diameters.
Progressive disease (PD)	
• SLD increased by at least 20% from the smallest value on study (including baseline, if that is the smallest).• SLD must also demonstrate an absolute increase of at least 5 mm. (2 lesions increasing from, for example, 2 mm to 3 mm, does not qualify).
Stable disease (SD)	
• Neither sufficient shrinkage to qualify for PR nor sufficient increase to qualify for PD.
Nonevaluable (NE)	
• One or more lesions cannot be evaluated because of missing data or poor image quality unless a convincing argument can be made that the contribution of the individual missing lesion(s) would not change the assigned time point response (eg, PD based on other findings).

Abbreviations: SLD, sum of the longest diameters.

Nontarget Lesion Response

Complete response (CR)	
• Disappearance of all extranodal nontarget lesions.• All lymph nodes must be nonpathological in size (<10 mm short axis).• Normalization of tumor marker level.
Non-CR/non-PD	
• Persistence of 1 or more nontarget lesions(s) and/or maintenance of tumor marker level above the normal limits.
Progressive disease (PD)	
• Unequivocal progression of existing nontarget lesions (subjective judgment by experienced reader).

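### Table 8-1 leaves dosed patients with no on-treatment tumour assessment out of the ORR denominator; if they are non-responders, the reported ORR exceeds the all-treated ORR by 1/(1-d)

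*Combined protocol and SAP*

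**What the plan says.** Table 8-1 in Section 8.2 defines the Efficacy population as participants who "received at least one dose of PCLX-001 and had at least one on-treatment tumour assessment will be included in the efficacy analysis". The Safety population in the same table is wider. It takes everyone with at least one dose, "whether prematurely withdrawn from the study or not, will be included in the safety analysis". The protocol names no denominator for ORR as such, but Section 3.5 lists ORR among the efficacy parameters, so the Efficacy population is its denominator by implication.

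On timing, Section 7.3 has solid-tumour lesions "assessed and reported at the end of every second cycle, starting at the end of Cycle 2", and sends lymphoma scans to Tables 7A and 7B. Footnote i of Table 7B sets the window at plus or minus "5 days from Day 28 of the even-numbered cycles".

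On handling patients who are never assessed, the protocol is silent. Section 8.4 reads "Descriptive statistics will be utilized to present study patient population and toxicity data" and does not mention response. The non-evaluable category in Appendix B applies where "One or more lesions cannot be evaluated because of missing data or poor image quality". That classifies lesions at a time point and does not say what to do with a patient who has no time point at all. Section 4.3 allows additional enrolment in an expansion cohort when dropout reaches 20%, so that 20 per indication can be evaluated for response. It does not say whether the dosed patients who left remain in any response denominator.

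**The concern.** Whether a patient is in the efficacy set depends on something that happens after dosing. To have a scheduled assessment, a patient must remain on study for roughly eight weeks. Many reasons for leaving sooner (toxicity, clinical deterioration, death) are treatment failures, and removing failures from the denominator pushes the response rate in one known direction.

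What is at stake is limited. Anti-tumour activity is the single secondary objective (Section 2), and the two expansion cohorts are opened to look for it (Section 3.5). ORR is also one of several inputs to the recommended Phase II dose (RP2D). No hypothesis test, response threshold or power calculation is attached to it.

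**Working it through.** **Plan's own figures.** Section 8.1 gives two expansion cohorts of 20, and 2 × 20 = 40 matches its stated total. The protocol states no target ORR, precision or expected early loss, so there is no ORR figure to reproduce.

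**Timing.** With 28-day cycles and no delay, Day 28 of Cycle 2 is study Day 28 + 28 = 56. The window of ±5 days gives Days 51-61.

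**Factor.** Let N be patients dosed, r responders, and d the share of dosed patients with no on-treatment assessment, all taken as non-responders.

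- Efficacy-set ORR = r / [N(1-d)]
- All-treated ORR = r / N
- Ratio = 1/(1-d) for any r > 0; with r = 0 both rates are 0%
- Absolute gap = all-treated ORR × d/(1-d)

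**Numbers.** The values of d and the 4 responders are assumptions; N = 20 is the Part B cohort size. Intervals are exact (Clopper-Pearson) 95%. The all-treated result is 4/20 = 20% (5.7-43.7%) throughout.

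| Unassessed of 20 | d | Ratio 1/(1-d) | Efficacy-set ORR (95% CI) |
|---|---|---|---|
| 2 | 10% | 1.11 | 4/18 = 22.2% (6.4-47.6%) |
| 4 | 20% | 1.25 | 4/16 = 25.0% (7.3-52.4%) |
| 6 | 30% | 1.43 | 4/14 = 28.6% (8.4-58.1%) |

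At d = 20% the absolute gap is 20% × 0.2/0.8 = 5 percentage points.

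**Relaxing the non-responder assumption.** Suppose unassessed patients would have responded at a fraction f of the rate p seen in assessed patients. The rate over all dosed patients is then p[(1-d) + d·f], and the efficacy-set ORR overstates it by 1/[(1-d) + d·f].

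| d | f = 0 | f = 0.5 | f = 1 |
|---|---|---|---|
| 10% | 1.11 | 1.05 | 1.00 |
| 20% | 1.25 | 1.11 | 1.00 |
| 30% | 1.43 | 1.18 | 1.00 |

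**The case against.** The strongest reply is that this is an openly declared response-evaluable set, consistent with the aim in Section 4.3 of 20 patients evaluable for response, in an uncontrolled Phase I study where response is descriptive. The factor 1/(1-d) is an identity against a comparator that the plan never promised. At f = 1 the efficacy set is unbiased, and the non-responder rule would itself understate ORR by the share d. This stands as a limit on weight. It does not remove the point, because early losses to toxicity or deterioration are unlikely to resemble assessed patients, and no part of the plan asks for the all-treated rate alongside.

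It is also fair that not every early exit is lost. Section 7.2 allows unscheduled visits, Section 7.3 allows PET-CT for lymphoma where it is standard of care, and a patient whose early progression is seen on a scan stays in the denominator. The entry criterion of at least 12 weeks' life expectancy (84 days, beyond Day 61) works against early death, though not against toxicity stops or withdrawal. All this makes d smaller by an unknown amount.

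Four stronger readings are tempting but not supported:

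- A reader might infer that membership of the set is itself ambiguous, because Appendix B accepts a "10 mm caliper measurement by clinical exam". That line defines measurable disease at screening. Section 7.3 ties response to CT or MRI for solid tumours and to radiological evaluation for lymphoma, and the row label in Table 7B, "Tumor assessment all tumors (CT or MRI", agrees.
- A reader might take the 20% in Section 4.3 as the expected d. It is a dropout trigger for optional extra enrolment, and a patient can drop out after a scan.
- A reader might infer distorted comparisons between groups. The study is non-randomised and uncontrolled, and no comparison of response between groups is planned.
- A reader might place Cohort A firmly inside or outside the RP2D review. Section 3.5 bases the RP2D on data from all parts of the study, yet opens Cohort A after the RP2D is set. The text does not settle it, and nothing here depends on it.

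**Conclusion.** The point holds as a cheap improvement. Following Table 8-1 as written gives an ORR above the all-treated ORR by exactly 1/(1-d) whenever there is at least one responder and the unassessed patients are non-responders.

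The direction is certain under those conditions, but the size is not, since the documents give no d. Over an assumed 10-30% the factor is 1.11-1.43, falling to 1.05-1.18 if unassessed patients would have responded at half the observed rate, and to 1 if they would have responded equally often. In the 20-patient example the shift lies well inside the confidence interval.

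A reader might infer that the trial's conclusions or error rates are compromised. The documents do not support that: ORR has no test or cut-off, and an all-treated rate can still be worked out if both counts are reported. What is affected is the reported activity estimate and one of several RP2D inputs.

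**What to change.** In Table 8-1, make the main ORR denominator all patients who received at least one dose, presented by cohort and dose. Count those with no on-treatment tumour assessment as non-responders, and report their number and reasons. Keep the present definition as a supportive set, labelled response-evaluable.

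In Section 4.3, add a sentence stating that dosed patients who left remain in the all-treated denominator if additional patients are enrolled.

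The cost is wording only, with no new data, visits or patients. The downside is that the main ORR is lower than the present one by the share d of its value (10-30% over the assumed range), and is conservative where withdrawal had nothing to do with disease or treatment. The supportive set shows by how much.

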8.4 Statistical Analyses

Descriptive statistics will be utilized to present study patient population and toxicity data.

8.5 Pharmacokinetic Analyses

PK parameters of PCLX-001 will be determined via non-compartmental analysis. Individual and mean serum PCLX-001 concentration versus time data will be listed by patient and tabulated by dose level. Graphical displays of PK data may also be provided.

Other PK variables will be summarized using descriptive statistics only. These will include:

- C_{\max}
- Minimum observed serum concentration (C_{\min}) at the beginning of Cycle 2 and at the beginning of every subsequent cycle where PK data are available
- Time to reach maximum serum concentration (t_{\max})
- AUC
- CL
- Volume of distribution (Vd)

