5.2 Dosage and Administration

PCLX-001 will be provided as an oral daily dose on a 28-day cycle. Doses should be taken around the same time each day, within a ± 3 hour window. PCLX-001 capsule(s) are to be taken by mouth and swallowed with approximately 250 ml of water, at least ninety minutes after eating solid food. After PCLX-001 is taken, the patient should wait 2 hours before eating solid food. Missed doses for any reason (i.e. outside of the allowable dosing window) will not be administered at a later time. In Part A, dose-escalation levels are provided in Section 3.3. PCLX-001 capsules are available in doses of 10 mg and 70 mg and the number of capsules will be calculated to ensure proper daily dosing is provided.

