5.3.1 Cycle 1 DLT Modifications for Part A Dose-Escalation Cohorts

If a patient experiences a treatment related hematological or non-hematological DLT (as defined in Section 3.2) during Cycle 1, the next dose of PCLX-001 will be delayed for up to 28 days for Part A. If the toxicity fails to resolve to CTCAE Grade ≤ 2 within 28 days, the patient should be withdrawn from study treatment but followed for safety until resolution.

If the toxicity resolves to CTCAE Grade ≤ 2 , re-treatment with PCLX-001 can be considered. Re-treatment of this patient should be at 1 dose level below the initial dose. Detailed dose modifications are described in Table 5-1. Patients experiencing any drug-related, clinically significant, non-hematological CTCAE Grade 4 toxicity will be withdrawn from study treatment but followed for safety until resolution. There will be no intrapatient dose escalation and no more than two dose reductions will be allowed.

Table 5-1: Dose Modifications of PCLX-001

Existing Dose (mg)	Modified Dose (mg)
280	210
210	140
140	100
100	70
70	40
40	20
20	10
10	Discontinue study drug

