5.3.2 Dose Modifications for HEMATOLOGIC Toxicities

For cycle 2 and beyond, Day 1 administration of PCLX-001 requires a platelet count of $\geq 75 \times 10^9/L$ and an absolute neutrophil count (ANC) of $\geq 1.5 \times 10^9/L$. CBC's drawn within 72 hours of treatment day may be used provided they meet parameters. However, if treatment parameters are not met, dose interruption will be made on the basis of blood counts taken the day of scheduled treatment. If counts are below this threshold, treatment will be delayed for 1 week and reassessed weekly until these parameters are met.

If a patient experiences a hematologic DLT in the preceding cycle OR if treatment is held for > 7 days due to neutropenia and/or thrombocytopenia, then the subsequent cycle will be administered at one lower dosing level. No more than two dose reductions will be allowed.

Patients should not receive prophylactic G-CSF for cycle 1. Subsequent use will be at the discretion of the treating physician and as per the ASCO guidelines on colony stimulating factors.

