7.4 Pharmacokinetics

7.4.1 Drug Measurements

In patients enrolled in Part A dose escalation, serial blood (plasma) samples will be collected at the time points shown in Table 7C to assess PK of PCLX-001. For patients enrolled in Part B dose expansion, serial blood (plasma) samples will be collected at the pre-dose time points shown in Table 7D.

Whenever possible, all efforts should be made to adhere to the blood-sampling schedules given in Tables 7C and 7D. However, based on practical considerations, the following time ranges are provided as guidance:

Pre-dose samples should be collected within 15 min before the administration of PCLX-001. For 0.5 hours post dose, the PK sample should be collected within \pm 6 minutes. Subsequent PK samples should be collected \pm 15 minutes of planned time point. Sampling times outside these suggested intervals will not be considered as protocol deviations. The date and time of actual blood sampling and dose administration will have to be documented in the eCRF because PK calculations will be based on the actual sampling times relative to dosing times.

Cumulated substantial deviations of sampling times and / or consecutive, missing PK samples may lead to an insufficient (inadequate) description of the plasma concentration vs. time profiles of PCLX-001, and thus affect the quality of the PK evaluation of the respective patient(s). In this case, these deviations should be classified as “important” and may lead as declared “validity findings” to the exclusion of the respective patient(s) from the PK analysis set.

Details on sampling procedures, sample storage, and shipment are documented in separate sample handling documentation.

Table 7C: Schedule of pharmacokinetic blood sampling time points in Part A Dose Escalation

Procedures	Study Treatment Period 1 Cycle = 28 days								
	Cycle 1					Cycle 2		Cycle 3/ Beyond	EOT Visit
Visit Identifier (Visit Window)	Day 1	Day 2	Day 8 (±2)	Day 15 (±2)	Day 22 (±2)	Day 1 (± 2)	Day 15 (±2)	Day 1 (±2)	
	X	X	X	X	X	X	X	X	X
Pharmacokinetics									
Pre-dose* (-15 min)	X	X	X	X	X	X	X	X	X
0.5 hour (± 6 min)	X			X					
1 hours (± 15 min)	X			X					
2 hours (± 15 min)	X			X					
4 hours (± 15 min)	X			X					
8 hours (± 15 min)	X			X					

*If patient is receiving a dose on that day

Table 7D: Schedule of pharmacokinetic blood sampling time points in Part B Dose Expansion

Procedures	Study Treatment Period 1 Cycle = 28 days								
	Cycle 1					Cycle 2		Cycle 3/ Beyond	EOT Visit

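### Section 8.5 summarises Cmin only at Day 1 of Cycle 2 and later, the day hematologic holds delay, so post-hold samples count as troughs while on-treatment Cycle 1 troughs are left out

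*Combined protocol and SAP*

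**What the plan says.** Four provisions meet on one day.

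- **Section 8.5** lists Cmin among the PK variables and ties it to samples "at the beginning of Cycle 2 and at the beginning of every subsequent cycle where PK data are available". It also promises that "concentration versus time data will be listed by patient and tabulated by dose level", without saying whether dose level means assigned or received.
- **Section 5.3.2** sets count thresholds for starting each later cycle ("For cycle 2 and beyond, Day 1 administration of PCLX-001 requires a platelet count of" a stated level, with an ANC condition as well). It continues: "If counts are below this threshold, treatment will be delayed for 1 week and reassessed weekly until these parameters are met". A hold of more than 7 days, or a hematologic DLT in the cycle before, lowers the next cycle by one dose level.
- **Table 7C** (Section 7.4.1) puts one condition on the pre-dose sample: "If patient is receiving a dose on that day". The table schedules Part A pre-dose samples on Cycle 1 Days 1, 2, 8, 15 and 22, Cycle 2 Days 1 and 15, and Day 1 of later cycles. Full profiles to 8 h are taken on Cycle 1 Days 1 and 15. Table 7D gives Part B pre-dose samples only: Cycle 1 Days 1 and 15, then Day 1 of each later cycle.
- **Section 5.3.1** covers a Cycle 1 DLT: "the next dose of PCLX-001 will be delayed for up to 28 days for Part A". Re-treatment is then one level lower, or the patient is withdrawn. Table 5-3 lets Grade 3 or 4 tumour lysis syndrome (TLS) restart at the target dose after discussion with the Medical Monitor.

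Section 8.2 excludes whole participants from the PK population for significant violations, deviations or incomplete data. Neither it nor Section 7.4.1 has a sample-level rule for a trough that follows held doses.

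**The concern.** A trough summary should describe concentration at the end of a dosing interval under continuous dosing. Section 8.5 takes it only on the day that Section 5.3.2 moves when counts are low. As the Table 7C footnote reads, the sample is not due on the scheduled day if the dose is held, but on the day dosing resumes. A genuine 24 h trough is thus replaced by a washout value. The error runs downward and is tied to toxicity.

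Such holds are foreseeable. Section 1.2.4 reports decreased hematopoiesis as part of the dose-limiting toxicity in both rats and dogs. The Day 1 thresholds (platelets 75, ANC 1.5, both × 10⁹/L) equal the ANC entry criterion for all patients and the platelet entry criterion for Dose Expansion in Section 4.1, so a small fall can trigger a hold.

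PK is a primary objective (Section 2), and Section 3.5 names available PK data among the inputs to the RP2D. Part B draws only pre-dose samples, so the trough is the exposure measure its schedule mainly supports.

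**Working it through.** The plan states no target, precision or sample size for Cmin, so there is no figure of its own to reproduce. The check asks how far a post-hold sample departs from a regular trough.

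**Inputs**
- Hold length H: at least 7 days, in weekly steps (5.3.2); up to 28 days after a Cycle 1 DLT (5.3.1).
- Half-life t: only animal oral values are given, 3.9 h in dogs and 5.7 h in mice (1.2.4). A human range of 4 to 72 h is assumed.
- Model: one compartment, first-order elimination (assumed).
- Dose steps: Table 5-1.

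**Step 1. Post-hold sample against regular trough.** A regular trough is drawn 24 h after the last dose. After a hold of H days the sample is drawn 24H hours later than that, so the ratio is f = 2^(−24H/t). For H = 7, f = 2^(−168/t):

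| t | f after 7 days |
|---|---|
| 12 h or less | at most 2^(−14), below 0.01% |
| 24 h | 2^(−7) = 0.8% |
| 48 h | 2^(−3.5) = 8.8% |
| 72 h | 2^(−2.33) = 19.8% |

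For H = 28 at t = 72 h, f = 2^(−9.33), about 0.2%; it is smaller for any shorter half-life.

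**Step 2. Effect on the mean.** With k post-hold values among n otherwise equal troughs, arithmetic mean ÷ true trough = (n − k + k·f)/n.
- n = 6, k = 1: 5/6 = 0.833 when f is near 0; (5 + 0.198)/6 = 0.866 at 72 h. The reduction is 13 to 17%.
- n = 6, k = 2: 4/6 = 0.667 when f is near 0; (4 + 2 × 0.198)/6 = 0.733 at 72 h. The reduction is 27 to 33%.

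Section 8.5 does not name the statistic. A geometric mean has ratio f^(k/n) and falls further: for k = 1 of 6, 0.445 at 24 h and 0.764 at 72 h. A median of 6 equal troughs would not move with one or two post-hold values.

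**Step 3. Cycle 1 DLT patients in the Cmin summary.** There are three usual outcomes.
- Withdrawn before Cycle 2: no Cmin.
- Hold runs into Cycle 2 Day 1: a washed-out value, as in Step 1.
- Restarted within Cycle 1: a value at the reduced dose, which by Table 5-1 is 50% (40 to 20 mg, 20 to 10 mg) to 75% (280 to 210 mg) of the assigned dose.

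A TLS patient restarted at the target dose is an exception and can give a valid trough.

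**Step 4. Are the unused samples usable?** After n daily doses the trough is 1 − 2^(−24n/t) of steady state. At Cycle 1 Day 8 (7 doses) that is about 100% for t up to 12 h, 99% at 24 h, 91% at 48 h and 80% at 72 h. At Day 15 (14 doses) and t = 72 h it is 1 − 2^(−336/72) = 96%.

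**The case against.** The strongest reply is that nothing is lost. The Cycle 1 pre-dose samples are collected, and Section 8.5 lists and tabulates all concentrations, not only those from Cycle 2. Dose and sampling times are recorded, so an analyst can recognise a washed-out sample. Cmax and AUC from the Part A profiles do not depend on the Cmin rule. Section 8.5 is descriptive, and no visible decision rule uses Cmin. All of this stands, and it makes the point one of summary definition and data handling. It does not repair the summary: a protocol-mandated hold is not a deviation, so a post-hold sample enters Cmin unflagged.

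Several stronger readings are tempting and should be resisted.

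- *All toxicity holds fall on Day 1.* Only the hematologic holds of 5.3.2 are tied to that day. Holds under 5.3.1 and 5.3.3 start at the next daily dose and can end mid-cycle, and 28 days is a ceiling.
- *DLT patients have no valid trough at all.* Any such patient in Part A still dosed at Cycle 1 Day 8, 15 or 22 has a trough at the assigned dose, reported under 8.5 though not as Cmin.
- *The RP2D rests on a trough-to-DLT model that this spoils.* Section 3.5 links PK/safety modelling to possible alternative schedules. For the RP2D it names only available PK data.
- *The dosing window is part of the defect.* Section 5.2 says "Doses should be taken around the same time each day, within a ± 3 hour window". That variation affects a trough at any visit and would remain after the change proposed here.

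**Conclusion.** The point holds as a defect in how Cmin is defined. Followed literally, Section 8.5 counts as troughs samples drawn after a week or more off drug, while leaving out on-treatment troughs that Tables 7C and 7D already collect. Where one patient of 6 is affected, the arithmetic mean Cmin falls by about 13 to 17%; where two are, by 27 to 33%.

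These sizes are conditional. They need a patient at that dose to be held at a Day 1, otherwise equal troughs, an arithmetic mean, first-order elimination and an assumed half-life of at most 72 h. They do not show that Cmin is biased at every dose level. MTD determination rests on Cycle 1 DLTs (3.2 and 3.3) and is untouched. The change is worth making because PK is a primary objective, the error is linked to toxicity, and the remedy is cheap.

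**What to change.** Reword the Cmin entry in Section 8.5 along these lines:

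- **Definition.** Cmin is the pre-dose concentration at any scheduled visit from Cycle 1 Day 8 onward. In Part A these are Cycle 1 Days 8, 15 and 22, Cycle 2 Days 1 and 15, and later Day 1s. In Part B they are Cycle 1 Day 15, Cycle 2 Day 1 and later Day 1s.
- **Condition.** The sample must follow uninterrupted daily dosing at the same dose for a minimum number of days, set from the observed half-life. Step 4 of the working shows why this number should wait for human data: Day 8 is ample at 24 h but not at 72 h.
- **Grouping.** Summarise by dose actually received.
- **Post-hold samples.** List them with time since last dose and keep them out of the Cmin summary.

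The cost is a wording change. No visit or sample is added, because the compliance diary (5.5) and the eCRF (5.5, 7.4.1) already capture dosing and sampling times. The small downside is that some Day 1 values leave the summary.
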